## 4 DATA ANALYSIS PLAN

### 4.1 OVERALL ANALYTICAL PLAN

All analyses will be performed on an intention-to-treat basis, which generally biases toward no difference. We will also perform per-protocol analyses where the assigned intervention was followed. We will first examine the data structure, distributions of the outcomes and explanatory variables, and potential missing data elements. Missing data will be imputed after examining the reason for missingness. For data that are missing completely at random or missing related to other collected covariates, we will use the multivariable imputation by chained equation (MICE) to impute data before fitting models.

The individual ICU is the unit of randomization, and the individual patient is the unit of analysis. In SW-CRT, the usual comparisons between two treatments need to be made over a differing time making standard group comparison-based methods biased and potentially ineffective. Therefore, we will use adjusted generalized linear mixed models (GLMM) for all primary and secondary outcomes, as delineated by Hussey and Hughes and others, to account for temporal and clustering effects typically encountered in SW-CRT designs. In these models, we will use the ICU as random effects. Time will be treated as random in the main analysis but will also be treated as fixed effects and interact with other covariates.

We will adjust all analyses for prespecified variables such as age, baseline eGFR, severity of illness as measured by the acute physiology and chronic health evaluation (APACHE)-III score, Elixhauser Comorbidity Index score, use or nonuse of mechanical ventilation, admission source, percentage of fluid overload before study enrollment, presence or absence of sepsis, baseline cardiovascular SOFA score and any other variable that are associated with outcome of  $UF_{NET}$  and had a between-group difference ( $P \leq 0.2$ ) on univariable analysis. We will assess the stability of final models using routine model diagnostics to identify potential outliers and/or influential observations. We will report both

adjusted and unadjusted analyses stratified by restrictive and liberal UFNET groups.

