### 4.2.1 THE BETWEEN-GROUP DIFFERENCE IN MEAN DELIVERED UFNET RATE

The primary objective is to measure a minimum of 0.52 mL/kg/h separation in the delivered patient mean UFNET rates between the restrictive and liberal UFNET rate groups. We chose between-group separation as a feasibility metric because it is a robust measure of adherence to complex protocols and has been used in ICU trials assessing the feasibility of frequently titrated interventions. Specifically, we reasoned that a larger study would not be feasible if the separation in the UFNET rates were less than 0.52 mL/kg/h. We chose 0.52 mL/kg/h as a clinically meaningful difference because our preliminary data indicated that a 0.50 mL/kg/h increase in UFNET rate is associated with increased mortality.

For between-group differences in delivered UFNET rates, we will report the patient-averaged UFNET rate with a corresponding 95% confidence interval. The patient averaged UFNET rate was the average of all hours for days where any UFNET was delivered. We will not include hours during which no fluid was removed during CKRT. We will use GLMM with a two-sided alpha of 0.05 to test the null hypothesis that the mean difference in the patient averaged delivered UFNET rate was less than 0.52 mL/kg/h after adjusting for the above prespecified variables.

We will also perform exploratory analysis in which we will examine between-group differences in peak (*i.e.*, maximum) delivered UFNET rates. We will also examine differences in longitudinal trajectories of mean delivered UFNET rate between the restrictive and liberal UFNET groups over time. We will perform subgroup analysis in which we will examine between-group differences in mean delivered UFNET rates among those with and without >10% fluid overload at enrollment; eGFR greater or less than 60mL/min/1.73m^2; duration of UFNET before enrollment (*i.e.*, greater or less than 6 hours); age  $\geq 65$  and  $< 65$  years; with and without sepsis; and baseline cardiovascular SOFA score  $\geq 3$  and  $< 3$ .

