## 5.3 APPENDIX C: SHELL TABLES

### 5.3.1 TABLE 1: CHARACTERISTICS OF PATIENTS AT BASELINE

	Characteristics	No. (%)		Unadjusted P value
		Restrictive (N= XX)	Liberal (N=XX)	
Age, years, median (IQR)				
Female sex				
Ethnicity				
White				
Black				
Hispanic				
Asian				
Native Hawaiian				
American Indian				
Other				
Prefer not to answer				
Actual body weight at hospital admission, Kilograms, median (IQR)				
Baseline serum creatinine, mg/dL, median (IQR)				
Estimated glomerular filtration rate, mL/min/1.73m  median (IQR)				
Elixhauser Comorbidity Index score				
Pre-existing conditions				
Hypertension				
Diabetes mellitus				
Chronic kidney disease				
Coronary artery disease				
Heart failure				
Liver disease				
Metastatic cancer				
Chronic pulmonary disease				
Primary diagnosis				
Cardiovascular				
Pulmonary				
Gastrointestinal				
Toxicology				
Infection or sepsis				
Neurologic				
Oncologic				
Other				
Etiology of acute kidney injury				
Sepsis				

	Characteristics	No. (%)		Unadjusted P value
		Restrictive (N= XX)	Liberal (N=XX)	
	Ischemic			
	Nephrotoxic			
	Multifactorial			
	Risk factors for fluid overload in the past week			
	Sepsis			
	Hemorrhage			
	Acute pancreatitis			
	Other			
	Source of admission			
	Home			
	Skilled Nursing Facility			
	Assisted Living Facility			
	Other			
	Admission category			
	Medical			
	Scheduled surgery			
	Emergency surgery			
	Clinical condition at study enrollment			
	Sepsis			
	APACHE-III score, median (IQR)			
	Cardiovascular SOFA score, median (IQR)			
	Vasopressor support			
	Mechanical ventilation			
	Fluid overload percentage			
	Median cumulative fluid balance at study enrollment, median (IQR) mL			
	Median UF rate at study enrollment, (IQR), mL			
	Oliguria/anuria			
	Urinary output, mL/24 hours, median (IQR)			
	Corticosteroid use			

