5.3.2 TABLE 2: PRIMARY AND SECONDARY OUTCOMES

	Outcomes	Unadjusted Analysis			Adjusted Analysis		
		Restrictive (N= XX)	Liberal (N=XX)	P value	Restrictive (N= XX)	Liberal (N=XX)	Estimated Effect of Intervention (95% CI)
Primary							
Delivered UF NET rate, mean (SD)							
Delivered UF NET rate, median (IQR)							
No. of participants with protocol deviation							
Recruitment rate per month per site							
Secondary							
Daily fluid balance excluding UF, mL, median (IQR)							
Cumulative fluid balance excluding UF, mL, median (IQR)							
Daily fluid balance including UF volume, mL, median (IQR)							
Cumulative fluid balance including UF volume, mL, median (IQR)							
Duration of kidney replacement therapy, days, median (IQR)							
Duration of mechanical ventilation, days, median (IQR)							
Organ failure free days, days, median (IQR)							
ICU length of stay, days, median (IQR)							
Hospital length of stay, days, median (IQR)							

	Outcomes	Unadjusted Analysis			Adjusted Analysis		
		Restrictive (N= XX)	Liberal (N=XX)	P value	Restrictive (N= XX)	Liberal (N=XX)	Estimated Effect of Intervention (95% CI)
	Kidney replacement therapy dependence at discharge among survivors						
	Hospital mortality						

\$ Adjusted for differences in age, baseline eGFR, APACHE-III score, Elixhauser Comorbidity Index score, mechanical ventilation, admission source, percentage of fluid overload, sepsis, and baseline cardiovascular SOFA score.

[figure not shown]

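### The P≤0.2 covariate rule in SAP 4.1 leaves the primary model open, and could shrink the measured separation if enrollment UFNET rates already reflect the ICU's strategy

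*SAP*

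**What the plan says.** SAP 4.1 opens its covariate rule with "We will adjust all analyses for prespecified variables such as age, baseline eGFR" and goes on to name nine variables in all. The same sentence then admits "any other variable that are associated with outcome of" UFNET "and had a between-group difference" at P≤0.2 on univariable analysis. It gives no criterion for association with the outcome and excludes no variable.

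SAP 4.2.1 tests the primary separation against 0.52 mL/kg/h "after adjusting for the above prespecified variables". It does not say whether variables picked up by the screen count among these.

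The footnote to the results shell (SAP Table 2) reads "Adjusted for differences in age, baseline eGFR, APACHE-III score, Elixhauser Comorbidity Index score, mechanical ventilation, admission source, percentage of fluid overload, sepsis" and ends with the baseline cardiovascular SOFA score. It lists the nine and nothing else.

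The baseline shell (SAP Table 1) has a row "Median UF rate at study enrollment, (IQR), mL", split by group, in a table with an unadjusted P value column. Protocol 8.2 collects both the ultrafiltration rate and the UFNET rate at baseline. Fluid removal may begin before enrollment: the Protocol excludes only patients with more than 48 hours of it, the SAP those with more than 24 hours. The two documents need to be reconciled on this.

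**The concern.** There are two problems, and the first does not depend on the second.

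**The primary model is not fixed in advance.** The words *such as* leave even the named list open, and the P≤0.2 clause lets unblinded data, including the outcome, decide the rest. The screen is also a poor match for the design. SAP 4.1 itself warns that standard group comparisons are biased in a stepped-wedge trial because the treatments are compared over different periods, yet it selects covariates by just such a comparison. Liberal patients come mostly from earlier periods, so a calendar trend alone can push a variable through.

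**The rule could admit a variable that assignment has influenced.** The strategy is set per ICU, is unblinded, and stays in force once the ICU has crossed over (Protocol 6.3.2). Training is aimed at the ICU's clinicians (Protocol 6.2), who also set removal rates before consent. If those rates drift toward the ICU's strategy, the enrollment rate carries part of the intervention's effect, and adjusting for it removes real separation. SAP 4.2.1 says that a larger study would not be feasible below 0.52 mL/kg/h, so near that value the covariate choice could change the conclusion.

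**Working it through.** **1. The plan's own figures.** Inputs: SD 0.75, ICC 0.01, two-sided alpha 0.05 (SAP 3.6; Protocol 9.1). With the Hussey-Hughes variance, 6 ICUs × 7 periods × 3 patients = 126 gives power 0.801 at 0.52, which reproduces the SAP. With 10 ICUs and 11 periods, the Protocol's 111 patients give power 0.808 at 0.53. The sample-size figures do not depend on the covariate rule; they supply the SD and ICC used below.

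**2. Chance of passing the P≤0.2 screen.** Let d0 be the true difference in enrollment UFNET rate between groups. The documents do not give it, so a range is shown. With 56 per group (Protocol 9.1) and an assumed SD of 0.75 for the enrollment rate:

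- standard error = 0.75 × √(1/56 + 1/56) = 0.142
- z = d0 / 0.142
- P(select) = Φ(z − 1.282) + Φ(−z − 1.282)

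| d0 (mL/kg/h) | 0 | 0.1 | 0.2 | 0.3 | 0.4 |
|---|---|---|---|---|---|
| P(select) | 20% | 31% | 56% | 80% | 94% |

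**3. Effect of adjusting.** If the delivered rate has slope β on the enrollment rate, the adjusted separation is D − β × d0. For D = 0.53:

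- d0 = 0.2: 0.53 − 0.3 × 0.2 = 0.47; 0.53 − 0.6 × 0.2 = 0.41
- d0 = 0.4: 0.53 − 0.3 × 0.4 = 0.41; 0.53 − 0.6 × 0.4 = 0.29

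**4. The rule as a whole.** The variable is not selected every time, so the rule was simulated with 2,000 trials per row. Each trial had 10 ICUs, 12 two-month periods (the first three all liberal), 112 patients, ICC 0.01 and fixed period effects. The enrollment rate entered the model if it differed between groups at P≤0.2 and was associated with the outcome at P≤0.05. The second cut-off is an assumption, because the SAP gives none. Both rates have SD 0.75, so the correlation equals β.

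| True separation | d0 | Correlation | Selected | Mean, always adjusted | Mean, under the rule | Mean, rate left out |
|---|---|---|---|---|---|---|
| 0.53 | 0 | 0.3 | 17% | 0.52 | 0.52 | 0.52 |
| 0.53 | 0 | 0.6 | 20% | 0.53 | 0.53 | 0.53 |
| 0.53 | 0.2 | 0.3 | 51% | 0.48 | 0.49 | 0.54 |
| 0.53 | 0.2 | 0.6 | 52% | 0.41 | 0.43 | 0.53 |
| 0.53 | 0.4 | 0.3 | 91% | 0.41 | 0.41 | 0.53 |
| 0.53 | 0.4 | 0.6 | 93% | 0.29 | 0.30 | 0.53 |
| 1.0 | 0.2 | 0.3 | 53% | 0.94 | 0.95 | 1.00 |
| 1.0 | 0.2 | 0.6 | 53% | 0.88 | 0.90 | 1.00 |
| 1.0 | 0.4 | 0.3 | 92% | 0.88 | 0.89 | 1.00 |
| 1.0 | 0.4 | 0.6 | 93% | 0.76 | 0.77 | 1.00 |

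At a true 1.0 with d0 = 0, selection was 13% to 22% and the mean stayed at 1.00.

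**The case against.** The strongest reply is that the causal link is not in the documents. A reader might infer that the enrollment rate is shaped by the ICU's strategy and that the rule will therefore tend to select it. No section says so. Study procedures start only after consent (Protocol 6.7). Protocol 7.1 and 7.2 describe how patients who arrive outside the assigned range are brought into it, so the plan expects arrival rates that do not match assignment. The contamination argument in Protocol 6.3.1 concerns patient-level randomization, not care before consent. Some patients will have little or no prior removal, which dilutes both d0 and β. The Table 1 row may not even be the net rate. All of this stands, and it is why the bias is stated as conditional.

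A reader might also take one pair of inputs, say d0 = 0.3 and slope 0.5, and report 0.53 − 0.5 × 0.3 = 0.38. That assumes adjustment every time. With 80% selection the average is about 0.53 − 0.80 × 0.15 = 0.41, and neither input comes from the documents.

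Nor do the documents support dismissing the enrollment rate as a covariate. Without spill-over it is a legitimate prognostic variable. Enrollment is unblinded and depends on the attending physician's judgment, so restrictive-period ICUs might enroll patients with slower prior removal. The unadjusted separation would then be too large, and adjustment would correct it. This stands, and it argues for a sensitivity analysis rather than a ban.

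Data-driven selection might suggest an inflated type I error. None was shown: with pure-noise candidates the simulated rate was 4.7% to 4.8%.

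Finally, a shell footnote cannot name variables not yet chosen, and unadjusted results are also reported. Both are fair. But the test specified in SAP 4.2.1 is the adjusted one, and three sections still leave its covariates unsettled.

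**Conclusion.** The point holds as a pre-specification defect with a conditional risk of bias. It is established from the text that the rule is open-ended and outcome-informed, that it screens without regard to period or cluster, that it bars nothing ICU assignment could influence, and that it does not match the Table 2 footnote. Whether screened-in variables enter the primary test is unclear, although SAP 4.1 says all analyses.

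The size of the bias rests on assumptions. With pre-enrollment differences of 0.2 to 0.4 mL/kg/h and correlations of 0.3 to 0.6, a true 0.53 averages about 0.49 to 0.30, below the 0.52 threshold. With no difference there is no attenuation. If the true separation is 1.0, the mean estimate stays at 0.77 or higher, so the point estimate still clears the threshold. The harm therefore matters mainly when the true separation is close to the threshold. The simulation follows the Protocol's 10-ICU design with fixed period effects, whereas the SAP describes six ICUs and treats time as random in its main analysis.

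**What to change.** In SAP 4.1, delete the P≤0.2 clause and the words *such as*, and state that the nine named covariates are the complete list. Use the same list in SAP 4.2.1 and the Table 2 footnote so that the three places agree. Report a model that also adjusts for the enrollment UFNET rate as a prespecified sensitivity analysis only, noting that it may either remove real separation or correct for differential recruitment.

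One detail needs settling when the list is closed: the SAP names APACHE-III, while Protocol 8.2 collects APACHE II.

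This is a change of text, with no new data and no change in sample size. The cost is a possible small loss of precision, or some residual imbalance in a prognostic variable outside the list.

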## 4.2 ANALYSIS METHODS FOR PRIMARY OUTCOMES

The three primary feasibility outcomes are as follows:

### 4.2.1 THE BETWEEN-GROUP DIFFERENCE IN MEAN DELIVERED UFNET RATE

The primary objective is to measure a minimum of 0.52 mL/kg/h separation in the delivered patient mean UFNET rates between the restrictive and liberal UFNET rate groups. We chose between-group separation as a feasibility metric because it is a robust measure of adherence to complex protocols and has been used in ICU trials assessing the feasibility of frequently titrated interventions. Specifically, we reasoned that a larger study would not be feasible if the separation in the UFNET rates were less than 0.52 mL/kg/h. We chose 0.52 mL/kg/h as a clinically meaningful difference because our preliminary data indicated that a 0.50 mL/kg/h increase in UFNET rate is associated with increased mortality.

For between-group differences in delivered UFNET rates, we will report the patient-averaged UFNET rate with a corresponding 95% confidence interval. The patient averaged UFNET rate was the average of all hours for days where any UFNET was delivered. We will not include hours during which no fluid was removed during CKRT. We will use GLMM with a two-sided alpha of 0.05 to test the null hypothesis that the mean difference in the patient averaged delivered UFNET rate was less than 0.52 mL/kg/h after adjusting for the above prespecified variables.

We will also perform exploratory analysis in which we will examine between-group differences in peak (*i.e.*, maximum) delivered UFNET rates. We will also examine differences in longitudinal trajectories of mean delivered UFNET rate between the restrictive and liberal UFNET groups over time. We will perform subgroup analysis in which we will examine between-group differences in mean delivered UFNET rates among those with and without >10% fluid overload at enrollment; eGFR greater or less than 60mL/min/1.73m^2; duration of UFNET before enrollment (*i.e.*, greater or less than 6 hours); age  $\geq 65$  and  $< 65$  years; with and without sepsis; and baseline cardiovascular SOFA score  $\geq 3$  and  $< 3$ .

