### **Sample Size/Interim Monitoring**

[figure not shown]
1. Using the sample size calculation for SW-CRT design, 111 patients will have 80% power at a two-sided alpha of 0.05 to reject the null hypothesis that the average UFNET rate was at least 0.53 mL/kg/h different between the two groups, using intra-cluster correlation coefficient of 0.01, at a standard deviation of 0.75, and assuming mean UFNET rate of 1.0 mL/kg/h. We will enroll 112 subjects or 56 patients per group.
2. The principal analysis will be intent-to-treat based upon randomization assignment.
3. The trial progress will be evaluated by an independent Data and Safety Monitoring Board (DSMB). Being a feasibility study there will be no interim analyses.

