## 9 STATISTICAL CONSIDERATIONS

**NOTE: Detailed statistical analysis plan (SAP) will be a separate document**

### 9.1 STATISTICAL METHODS

The primary feasibility outcomes are between-group difference in mean  $UF_{NET}$  rate, protocol adherence, and recruitment rate. The primary objective of this feasibility trial to measure a minimum of 0.53-0.57 mL/kg/h separation in the delivered patient mean  $UF_{NET}$  rates between the restrictive and liberal  $UF_{NET}$  rate groups. We estimated that, if each of the 10 ICUs enrolled a minimum of 0.93 patient per 2 months for 24 months, we would have a total of 111 patients. Using the sample size calculation for SW-CRT design, we estimated that 111 patients will have 80% power at a two-sided alpha of 0.05 to reject the null hypothesis that the average  $UF_{NET}$  rate was at least 0.53-0.57 mL/kg/h different between the two groups, using intra-cluster correlation coefficient of 0.01, at a standard deviation of 0.75, and assuming mean  $UF_{NET}$  rate of 1.0 mL/kg/h (Table 6). After accounting for a very small attrition rate, we plan to recruit from each of the 10 ICUs: 1 patient per 2 months for 24 months for a total of 112 subjects or 56 patients per group.

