### 3.6 SAMPLE SIZE AND MONITORING

1. Using the sample size calculation for stepped wedge cluster randomized trial (SW-CRT) design, 126 patients will have 80% power at a two-sided alpha of 0.05 to reject the null hypothesis that the average  $UF_{NET}$  rate was at least 0.52 mL/kg/h different between the two groups, using intra-cluster correlation coefficient of 0.01, at a standard deviation of 0.75, and assuming mean  $UF_{NET}$  rate of 1.0 mL/kg/h. After accounting for a potential 10% attrition rate, the sample size was increased to 144 subjects or 72 patients per group.
2. The principal analysis will be intent-to-treat based upon randomization assignment.
3. The trial progress will be evaluated by an independent Data and Safety Monitoring Board (DSMB). Being a feasibility study there will be no interim analyses.

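### The 80% power quoted for UFNET separation is not the power of the test in SAP 4.2.1: the nulls run in opposite directions, and no rule says what is compared with the threshold

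*SAP*

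**What the plan says.** SAP 4.2.1 uses a GLMM at two-sided alpha 0.05 to "test the null hypothesis that the mean difference in the patient averaged delivered UF NET rate was less than 0.52 mL/kg/h". Rejecting that null would show enough separation.

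SAP 3.6 says that "126 patients will have 80% power at a two-sided alpha of 0.05 to reject the null hypothesis" that the average "rate was at least 0.52 mL/kg/h different between the two groups, using intra-cluster correlation coefficient of 0.01". Read literally, rejecting that null would show too little separation. The protocol has the same direction: its section 4 sample-size item claims 80% power to "reject the null hypothesis that the average UF NET rate was at least 0.53 mL/kg/h different between the two groups", and section 9.1 repeats it with a range ("rate was at least 0.53-0.57 mL/kg/h different between the two groups, using intra-cluster correlation coefficient of 0.01"). Protocol Table 6, by contrast, presents 0.53 and 0.57 as detectable differences.

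SAP 4.2.1 also sets a target for the measured value ("The primary objective is to measure a minimum of 0.52 mL/kg/h separation in the delivered patient mean") and promises an interval ("we will report the patient-averaged UF NET rate with a corresponding 95% confidence interval"). It says a larger study would not be feasible below 0.52. Protocol 5.8.1 puts that limit at 0.5, while the protocol's primary outcome asks for at least 0.53.

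**The concern.** Separation is the first of three primary feasibility outcomes, and both documents tie it to whether a larger trial can go ahead. Two things are unsettled.

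- **Which test the 80% describes.** A reader of SAP 3.6 followed by 4.2.1 would take 80% as the power of the 4.2.1 test. A test against a margin of 0.52 cannot have 80% power when the true separation is 0.52. At that point its rejection rate is its one-tail error rate.
- **What decides success.** The thresholds exist, but the plan does not say whether the point estimate, a confidence limit or the hypothesis test is compared with them. A separation above the threshold but below the test's cut-off would meet the stated outcome and still fail to reject the SAP 4.2.1 null. Choosing between these readings after seeing the data would make the result of a primary outcome post hoc.

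**Working it through.** **Inputs (SAP design).** N = 126, SD 0.75, ICC 0.01, two-sided alpha 0.05 and power 80% come from SAP 3.6. Six ICUs and steps 0 to 6 come from SAP Appendix D, Figure 3. That is 6 × 7 = 42 cells and 126/42 = 3 patients per cell.

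**Model.** Stepped-wedge mixed model on cell means, with a random ICU intercept, fixed period effects and no covariates. The between-ICU variance is 0.01 × 0.75² and the within-ICU variance is 0.99 × 0.75². The generalised least-squares standard error of the treatment effect is **0.1855**.

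**Step 1: reproduce the plan's figure.**
- Detectable difference against zero = (1.960 + 0.842) × 0.1855 = **0.520**, which is the SAP's 0.52.
- Power at 0.52 against zero = Φ(0.52/0.1855 − 1.96) = 80.1%.
- An individually randomised comparison, or a model without period effects, gives about 97% instead. The stated 80% is therefore a fixed-time calculation against a null of zero.

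**Step 2: the test written in SAP 4.2.1.** I read it as rejecting when the lower limit of the two-sided 95% CI exceeds 0.52.
- Observed separation needed = 0.52 + 1.96 × 0.1855 = **0.88**.
- True separation for 80% power = 0.52 + 2.802 × 0.1855 = **1.04**.
- Power at a true separation d = Φ((d − 0.52)/0.1855 − 1.96):

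| True separation | Power |
|---|---|
| 0.52 | 2.5% |
| 0.75 | 24% |
| 1.00 | 73% |
| 1.25 | 98% |

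**Step 3: the planned main model.** SAP 4.1 treats time as random. The documents give no time variance, so I assumed 0 to 0.05 (mL/kg/h)², still unadjusted. The SE is then 0.1358 to 0.1608.
- Cut-off: 0.52 + 1.96 × SE = 0.79 to 0.84.
- 80% point: 0.52 + 2.802 × SE = 0.90 to 0.97.

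**Step 4: the protocol's figures.** With N = 111, 10 ICUs and fixed time, the result depends on the number of windows.
- *11 windows (assumed).* SE 0.1872 gives 0.525 at ICC 0.01, and SE 0.2015 gives 0.564 at ICC 0.1. These are close to Table 6's 0.53 and 0.57.
- *13 windows.* Protocol 6.3.2 has six liberal months (three two-month windows), then one ICU crossing every two months. If all ten cross singly on that schedule, 3 + 10 = 13 windows are needed. SE 0.2028 gives a detectable difference of 0.568, and power at 0.53 is Φ(0.53/0.2028 − 1.96) = 74.3%.
- Section 9.1's accrual assumption ("if each of the 10 ICUs enrolled a minimum of 0.93 patient per 2 months for 24 months") covers 24/2 = 12 windows, one short of that. Section 6.3.2 also allows earlier crossover once 10 patients are enrolled, so the layout is not fixed.
- The one-sided rows of Table 6 (0.57 and 0.63, N = 126) were not reproduced. The SAP layout gives 0.461 and 0.505 one-sided.

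**The case against.** The strongest reply is that this is a wording problem in a feasibility trial. The at-least null reads as the alternative put where the null belongs, nobody's treatment depends on it, and the arms are meant to be far apart: 0.5-1.5 against 2.0-5.0 mL/kg/h, with midpoints of 1.0 and 3.5. At a true separation of 1.25 the SAP 4.2.1 test already has about 98% power. That stands, and it limits the severity.

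A reader might therefore infer the opposite from the 2.5% and 1.04 figures, namely that the trial is underpowered for separation. The documents do not support that. They state no expected separation, and the separation the target ranges aim for is well beyond 1.04. The reply still does not remove the point. The nearest edges of the two ranges are only 2.0 − 1.5 = 0.5 apart, and clinicians may lower, hold or override the rate (protocol 7 and 7.4.1), so an observed value between the threshold and the cut-off is possible.

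A second fair reply is that 0.88 and 1.04 use the planning standard error, not that of the random-time, covariate-adjusted main analysis. This also stands. Random time alone lowers them to about 0.79-0.84 and 0.90-0.97, and useful covariates would lower them further.

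Third, no passage states that the null was zero. For the SAP the match to 0.520 is close enough to rely on. For the protocol it remains an inference from Table 6's title and an assumed 11 windows.

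Finally, the SAP describes 6 ICUs and the protocol 10. That mismatch is a separate matter. Updating the SAP to the protocol's design would not cure this point, because the protocol carries the inverted null too.

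**Conclusion.** The point holds and should be fixed before analysis. It does not threaten the trial's validity.

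- **Certain from the text:** SAP 4.2.1 and SAP 3.6 state nulls in opposite directions. The protocol shares the SAP 3.6 direction. The thresholds of 0.5, 0.52 and 0.53 come without a rule saying which quantity is compared with them.
- **Well supported for the SAP design:** the 80% is power to detect 0.52 against zero, so it is not the power of the SAP 4.2.1 test. With fixed time and no covariates that test needs about 0.88 observed and reaches 80% power at about 1.04 true. Under random time with the assumed variances, the figures are 0.79-0.84 and 0.90-0.97.
- **Inference only for the protocol design:** its 0.53 fits a zero null on 11 windows but not on 13.

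In practice, an observed separation between the threshold and roughly 0.8-0.9 would meet the stated outcome without rejecting the SAP 4.2.1 null.

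**What to change.** Correct the inverted null in protocol sections 4 and 9.1 and in SAP 3.6. Then use one null, one threshold and one decision rule in both documents. Either option works:

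- **(a) Null of zero.** Remove the 0.52 margin from the null in SAP 4.2.1. Keep 80% power at the detectable difference, recomputed for the design actually run. State the feasibility threshold as a separate rule on the estimate and its 95% CI.
- **(b) Margin null.** Keep the margin, and declare it met if the lower limit of the two-sided 95% CI exceeds it. Restate the 80% power as applying at the true separation recomputed for the design and model actually used. For the SAP design with fixed time and no covariates that is about 1.04.

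Either way, give the layout, the time model and the adjustment behind each power figure.

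The cost is wording in four sections and one recalculation, with no extra patients. Option (b) carries a less favourable stated power.
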